## 10.6.2. Study Population

Demographics and Baseline Characteristics	
Age	

 
Age will be calculated based on the Pre-Screening Visit date (or Screening, if pre-screening not performed).
 
Only year of birth is collected on the eCRF. Birth date will be imputed as follows: 
 
Any participant with a missing day and month will have this imputed as '30th June'.
 
All participants with imputed age of 17 or 18 years will be source data verified, and presence / absence of protocol deviation on the inclusion criteria #1 will be taken into consideration in the derivation for the analysis variable age.
 
 
 
Birth date will be presented in listings as 'YYYY'.
 
	
Age at Onset	

 
This will be derived as age at pre-screening visit-duration of asthma
 
If a participant has age of onset of <0 this will be queried by data management
 
As we do not collect date of birth to the exact date negative values could occur. In these cases, the age of onset will be set to 0.
 
Age of onset will be presented in years. If the calculation results in a decimal due to duration of asthma being collected in years and months, the "floor" of the calculated value will be taken.
 
	
Body Mass Index (BMI)	

 
Calculated as Weight (kg) / Height (m)
 
	
Clinic Spirometry Assessment	

At Visit 1, if the spirometry assessment is repeated for a given participant to meet the eligibility criteria on the reversibility, the repeated spirometry data will be used for that visit.
	
ACQ	

 
Details of how to score the ACQ are provided in the Asthma Control Questionnaire, Background, Administration and Analysis, April 2008.
 
At baseline, ACQ-5 will be derived from items 1-5 of ACQ-6 performed at the randomization visit (Visit 2).
 
For further information on ACQ, see Section 10.6.3.
 
	
Cardiovascular History and Risk Factor	

Cardiovascular history and risk factors will be assessed at Visit 1. Participants with one or more of the following terms recorded as either current or past medical conditions at Visit 1 are considered to have cardiovascular history/risk factors:
 
 
Cardiovascular history 
 
arrhythmia,
 
congestive heart failure,
 
coronary artery disease,
 
myocardial infarction,
 
cerebrovascular accidents,
 
 
 
Cardiovascular risk factors 
 
hypertension,
 
diabetes mellitus
 
 
 
	

Demographics and Baseline Characteristics	
Age	
	
 
hypercholesterolemia.
 

Pneumonia History	
	
 
Pneumonia history will be assessed at Visit 1. Participants with pneumonia recorded as either current or past medical condition should also report the number of pneumonia episodes in the past 12 months and the number of pneumonia episodes requiring hospitalization over the past 12 months. This information will be summarized.
 

Treatment Compliance	
	
 
Treatment compliance will be assessed for the run-in period and double-blind treatment period.
 
If a dose counter start count is missing then it will be assumed to be 30 for the Ellipta DPI (e.g., such as for the open-label therapy dispensed during double-blind treatment period). If a dose counter stop value is missing then number of doses received will be set to missing for that container.
 
For the run-in phase (containers are to be returned prior to or on randomized study drug start date), percentage compliance to FF via ELLIPTA will be calculated as follows:
 

$$\frac{\text{dose counter start value} - \text{dose counter stop value}}{\text{run in treatment stop date} - \text{run in treatment start date} + 1} * 100$$

If more than one container is dispensed during run-in and are returned prior to or on randomized treatment start date, the number of doses received by each participant will be calculated as the sum of (dose counter start value – dose counter stop value) over all inhalers dispensed. If the date of container returned is > date of randomized treatment start date then the number of FF doses received will be set to missing for that container. For participants who were not randomized or were randomized in error and not treated, containers should be returned prior to or on the date of Visit 2.

- For each of the FF and double-blind containers dispensed during the double-blind treatment period, the actual total number of doses received by each participant will be calculated as the sum of (dose counter start value – dose counter stop value) over all inhalers dispensed to the participant during the double-blind treatment period, and percentage treatment compliance will be calculated as follows:

$$\frac{\text{Total number of doses received}}{\text{Treatment stop date} - \text{Treatment start date} + 1} * 100$$

Treatment compliance calculations for FF during the double-blind treatment period will not be adjusted in the case where a patient has not returned their run-in medication prior to randomization and continue use into the double-blind treatment period. Treatment compliance will be based only on the returned devices prior to or at end of study/early

withdrawal visit that were dispensed during the double-blind treatment period.

- Overall compliance will be categorized as follows:
  - < 50 %
  - ≥50 % to < 80 %
  - ≥80 % to < 95 %
  - ≥95 % to ≤105 %
  - >105 % to ≤120 %
  - >120 %.
- If a participant receives a treatment other than the randomized treatment during the study, the compliance will still be calculated using data from all containers received and overall exposure start and stop dates

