## 2.3. Study Design

Overview of Study Design and Key Features	
205832 Study – UMEC (62.5 mcg) vs UMEC (31.25 mcg) vs Placebo 	

N=384 randomised
 
Population: Asthma
 
Open label ICS FF 100 mcg
	

Study population (Asthma)
 
Not well controlled Asthma ACQ 6 threshold >0.75 prior to randomization at Visit 2
	
Endpoints
 
Primary: Mean change from baseline in clinic trough FEV1 at week 24. Secondary: Mean change from baseline in clinic FEV1 at 3 hours post dose at week 24.

Design Features
	
 
This is a phase IIb, randomized, double-blind, 3-arm parallel group study, comparing the efficacy, safety and tolerability of UMEC (62.5 mcg and 31.25 mcg) administered once-daily in participants with asthma that is not well controlled (i.e. participants with an ACQ-6 total score >0.75 at Visit 2 [the Randomization Visit] despite treatment with maintenance ICS).
 
The target total number of randomized participants is approximately 384, with 128 participants randomized to each of the 3 double-blind treatment arms. All participants will be on a background therapy of FF 100mcg administered daily.
 
Participants who permanently discontinue study treatment are not required to withdraw from the study. Participants who have permanently discontinued study treatment and have not withdrawn consent are encouraged to continue in the study and complete all remaining protocol specified clinic visits.
 

Dosing
	
 
The double-blind treatment will be delivered via an ELLIPTA DPI once daily in the morning during the study treatment period. The open-label FF 100mcg will be delivered via an ELLIPTA DPI once daily following the double-blind treatment.
 
The duration of the treatment period is 24 weeks.
 

Overview of Study Design and Key Features	
Time & Events	
 
Refer to Appendix 2: Schedule of Activities
 

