### 10.7.2. Handling of Missing Data

Element	Reporting Detail
General	
 
Missing data occurs when any requested data is not provided, leading to blank fields on the collection instrument: 
 
These data will be indicated by the use of a "blank" in participant listing displays. Unless all data for a specific visit are missing in which case the data is excluded from the table.
 
Answers such as "Not applicable" and "Not evaluable" are not considered to be missing data and should be displayed as such.
 
No imputation will be made for any missing numerical data, except in the sensitivity analysis of primary endpoints to assess the impact of missing data on study results. Missing data will generally not be considered in the calculation of percentages (i.e., the denominator will not include participants who have missing data at a given time point).
 
 
 

Spirometry	
 
When spirometry has been performed but the reading was unacceptable, a record in the database will indicate that the spirometry was performed but all data will be missing and will not be included in listings or summary displays.
 

Responder analyses	
 
Participants with a missing baseline will have responder status as missing.
 
Participants with missing data at the analysis timepoint, regardless of treatment status, will be considered as a non-responder.
 

Element	Reporting Detail
	
 
For ACQ/SGRQ/AQLQ, participants that have withdrawn from study prior to the visit in question will be imputed as non-responders at all visits after early withdrawal visit where the assessment was expected to be performed.
 

Treatment compliance	
 
For the run-in phase, if date open-label FF 100 ELLIPTA™ DPI device returned is > randomized treatment start date (or Visit 2 for participants who are not treated) date then compliance is set to missing for that container.
 
If a dose counter start count is missing then it will be assumed to be 30 for the ELLIPTA™ DPI. If any dose counter stop is missing then the number of doses received will be set to missing for that container.
 

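### Compliance in the treatment period counts doses only from returned inhalers but divides by the whole period, so participants with an unreturned inhaler are reported as less compliant than they were

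*SAP*

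**What the plan says.** Section 10.6.2 (Treatment Compliance) gives one formula for double-blind treatment and for open-label FF in the treatment period.

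- **Numerator, general statement:** dose-counter start minus stop, summed "over all inhalers dispensed to the participant during the double-blind treatment period".
- **Numerator, restriction a few lines later:** "Treatment compliance will be based only on the returned devices prior to or at end of study/early" withdrawal visit, and among those only devices dispensed in the double-blind period.
- **Denominator:** treatment stop date minus treatment start date plus 1, with no adjustment for devices that give no count.
- **No stop count:** "If a dose counter stop value is missing then number of doses received will be set to missing for that container". Section 10.7.2 repeats this: "If any dose counter stop is missing then the number of doses received will be set to missing for that container". Neither place says what then happens to the participant's total.
- **No start count:** "it will be assumed to be 30 for the Ellipta DPI".
- **FF carry-over:** FF compliance in the treatment period is expressly left unadjusted when a participant keeps using the run-in inhaler after randomization. A run-in inhaler returned after treatment start is set to missing for the run-in calculation, so the doses taken from it after randomization enter neither figure.

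Results are grouped as below 50%, 50 to <80%, 80 to <95%, 95 to 105%, above 105 to 120%, and above 120%.

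**The concern.** Numerator and denominator should cover the same days. Here an inhaler not handed in by the final visit adds nothing to the top, while the days it supplied stay in the bottom. The participant's result falls because a device was not returned, whatever was inhaled. For an unreturned device the error can only go downward.

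Compliance is reported in Table 1.40 and Listing 13. If umeclidinium shows little effect, or the two doses look alike, readers will turn to that table to judge whether treatment was taken. A fully adherent participant who appears in the 80 to <95% or 50 to <80% group misinforms that judgement.

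**Working it through.** The plan states no numerical compliance result, so there is no figure to reproduce. The check applies its formula to a participant who takes every dose.

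**Inputs**
- Once-daily dosing (section 2.3): "The double-blind treatment will be delivered via an ELLIPTA DPI once daily in the morning".
- Duration (section 2.3): "The duration of the treatment period is 24 weeks", so 24 × 7 = 168 days. Counting the Day 169 clinic dose gives 169.
- 30 doses per inhaler (section 10.6.2).
- Dispensing at Visits 2, 3 and 4 (Days 1, 29 and 85), with the last visit on Day 169 (section 10.2.1). The intervals are 28, 56 and 84 days.

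**Unreturned inhalers.** Let T be days on treatment and L the doses taken from unreturned inhalers. The reported value is (T − L)/T, and the participant's actual compliance is T/T = 100%.

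| Case | Calculation | Reported | Group |
|---|---|---|---|
| One inhaler, 30 doses | 138/168 | 82.1% | 80 to <95% |
| Same, 169 days | 139/169 | 82.2% | 80 to <95% |
| One inhaler, 28 doses (all that the first interval needs) | 140/168 | 83.3% | 80 to <95% |
| One inhaler, 24 doses (assumed) | 144/168 | 85.7% | 80 to <95% |
| Two inhalers, 30 doses each | 108/168 | 64.3% | 50 to <80% |

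The result barely moves within the −5/+2 day visit window: 134/164 = 81.7% and 141/171 = 82.5%.

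**Shorter treatment.** The same loss weighs more: 55/85 = 64.7% at 85 days and 27/57 = 47.4% at 57 days. Since 120/150 = 80.0%, one fully used but unreturned inhaler puts an adherent participant below 80% whenever treatment lasts fewer than 150 days.

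**Returned inhaler with no stop count.** Doses for that container are missing. If the sum skips it, the figures are those in the table. If missing carries through the sum, overall compliance is missing and nothing is understated. The plan does not choose.

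**FF carry-over.** The run-in lasts 2 weeks (section 2.3). Assuming one 30-dose run-in inhaler used daily for 14 days, 30 − 14 = 16 doses remain. If they are used after randomization, FF compliance is (168 − 16)/168 = 152/168 = 90.5%, even with every treatment-period device returned and full adherence.

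**The case against.** **Missing is not zero.** Sections 10.6.2 and 10.7.2 set doses to missing for a container with no stop count. A reader might infer that an unreadable counter is counted as no doses taken; the documents do not say so. This stands, and that case is an ambiguity to resolve.

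**The returned-devices sentence may be narrower.** It directly follows the FF carry-over sentence and could be read as saying only that run-in devices do not count. Its wording, however, speaks of treatment compliance in general and imposes two conditions, return by the final visit and dispensing in the double-blind period. On the narrow reading an unreturned inhaler would simply have no stop count, and the skip-or-propagate question would be open for it too. The text would still need repair.

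**FF carry-over is disclosed.** True, but the disclosed choice leaves the understatement in place without flagging the participants concerned.

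**Section 10.6.1 uses another rule.** There an unreturned container is assumed fully used, all 30 doses. A reader might call this a contradiction. It is not: that rule decides which treatment a participant is taken to have received after a misallocation, a different purpose.

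**The impact is small.** Compliance defines no analysis population and enters no efficacy model, no per-protocol analysis is planned (section 10.1), and the primary strategy is treatment policy (section 7.1.4). Treatment status (Tables 1.2 and 1.3) and exposure (Table 3.2, Figure 3.1) give readers other evidence. The derivation is the same in all arms. All of this stands and limits the point to descriptive output.

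**Conclusion.** The point holds for unreturned inhalers. Taken as written, the rule reports a fully adherent 24-week participant with one unreturned, fully used inhaler as about 82% compliant, or about 83% to 86% if that inhaler supplied 24 to 28 doses. Two such inhalers give about 64%. For returned inhalers without a stop count the same result follows only if missing containers are skipped. For FF, a carried-over run-in inhaler gives about 90% under the 16-dose assumption.

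These figures assume perfect adherence, which is why 100% is the right answer in each; for a real lost inhaler its use is unknown. A reader might infer that Table 1.40 as a whole will run systematically low. The documents do not support that: only participants with an uncounted device or a carried-over run-in inhaler are affected, and the plan gives no frequency for either. No efficacy conclusion depends on the figure. It is nonetheless a stated rule that gives a wrong value in a planned table and is easily corrected.

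**What to change.** 1. Reconcile the two statements of the numerator in section 10.6.2 (all dispensed inhalers, or returned ones only), and state in sections 10.6.2 and 10.7.2 whether a container with missing doses is skipped or makes the total missing.
2. Choose one treatment of uncounted containers:
   - set overall compliance to missing when any container dispensed in the period has no usable count, and report the number of such participants per arm; or
   - reduce the denominator by up to 30 days per uncounted container, which restores 138/138 = 100% in the one-inhaler case (140/140 = 100% if it supplied 28 doses and 28 days are removed).
3. Do not remove the time from dispensing to return instead. Day 85 to Day 169 is 84 days and needs three 30-dose inhalers. If one of them is uncounted, removing the whole interval gives 138/(168 − 84) = 138/84 = 164%. An inhaler that is never returned has no return date.
4. Treat participants with a carried-over run-in FF inhaler in the same way for FF, or flag them in Table 1.40 and Listing 13.

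The cost is SAP wording and a change to one derivation; no new data are needed. The downside is that some participants become missing for compliance or are assessed over a shorter period, so the number affected should be shown beside the result.

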### 10.6.3. Efficacy

Spirometry
Trough FEV1 and FVC

 
The trough value for FEV1 at Weeks 4, 12, and 24, visit is the value of the pre-dose (prior to taking the morning dose of study treatment) assessment in Liters (L).
 
Predicted percent normal FEV1: Predicted values will be based upon the European Respiratory Society (ERS) Global Lung Function Initiative [Quanjer, 2012]
 

Post-dose FEV1

 
The post-dose value for FEV1 at Week 24 or at the EW visit is the assessment value approximately 3 hours after administering the study medication and measured in Liters.
 

Asthma Exacerbations

 
Each asthma exacerbation will be categorized based on severity as follows: 
 
Moderate: 
 
Deterioration in asthma symptoms, deterioration in lung function, or an increased rescue bronchodilator use lasting for at least 2 days or more, but will not be severe enough to warrant systemic corticosteroid use for 3 days or more and/or hospitalization.
 
An event that, when recognized, should result in a temporary change in treatment, in an effort to prevent the exacerbation from becoming severe.
 
 
 
Severe: 
 
The deterioration of asthma requiring the use of systemic corticosteroids (tablets, suspension or injection) for at least 3 days, OR an inpatient hospitalization or emergency department visit because of asthma, requiring systemic corticosteroids
 
 
 
 
 
Exacerbations separated by less than 7 days will be treated as a continuation of the same exacerbation.
 
The duration of an exacerbation will be calculated as exacerbation resolution date or date of death - exacerbation onset date + 1.
 
On- and Post-Treatment Exacerbations: The time to first exacerbation will be calculated as exacerbation onset date of first exacerbation – date of start of treatment + 1. Participants will be represented from their Day 1 date up to and including the start date of their first exacerbation or up to and including the end of study (EOS) date (or early withdrawal date) + 1 day. Participants that have not experienced an exacerbation will be censored at EOS or early withdrawal + 1 day.
 

Asthma Control Questionnaire (ACQ)
General

 
All 6 items of ACQ have response on 0-6 ordinal scale (0=no impairment/limitation, 6=total impairment/ limitation). The total score is calculated as the average of all non-missing item responses [Asthma Control Questionnaire, Background, Administration and Analysis,
 

Spirometry
April 2008].

Only one of the first five item responses are allowed to be missing in calculating the total scores for all versions of ACQ.

If the language of the ACQ differs between visits, the following rules will be applied:

If the language at Visit 1 and Visit 2 are the same, but the language at a post-randomization visit differs, all ACQ scores at the post-randomization visit and all subsequent visits will be set to missing.

If the language at Visit 2 is the same as the language at post-randomization visits, but this differs from the language at Visit 1, the Visit 1 ACQ scores will be set to missing and change during the screening/run-in period will not be calculated.

If the language at Visit 2 differs from both the language at Visit 1 and the language at post-randomization visits, all ACQ scores for all visits will be set to missing.

If the language is missing at any visit (including baseline) and is the same at all non-missing visits, the language at the missing visit will be assumed to be unchanged.

ACQ-6 is performed at Visit 1 (screening) and Visit 2 (randomization) only and is primarily used for inclusion/exclusion criteria. ACQ-5 is derived at baseline from the ACQ-6 performed at Visit 2 and performed at all post randomization visits. ACQ-5 forms the basis of the efficacy evaluation.

Responder Status according to ACQ Total Score

A participant will be considered a responder according to ACQ-5 total score if their ACQ-5 total score has decreased at least 0.5 units from the baseline ACQ-5 total score.

A participant will be considered a non-responder if their ACQ-5 total score has decreased by less than 0.5 units, has not changed, or has increased compared to baseline.

Missing data will be handled as detailed in Section 10.7.2.

ACQ Control Category


Control categories are defined as:

Well controlled: <math>\leq 0.75</math>

Partially controlled: <math>0.75 < \text{ACQ score} < 1.5</math>

Inadequately controlled: <math>\geq 1.5</math>

St. George's Respiratory Questionnaire (SGRQ)	
General	

• Details for how to score the SGRQ, including handling of missing data, are outlined in the SGRQ manual (June 2009).

• Changes from baseline in domain and total score will be calculated for the converted scores.

• If the language of the SGRQ conducted at a post-treatment visit is different to the language used at Day 1 baseline, all SGRQ scores at that visit and all subsequent visits will be set to missing.

• If the language is missing at any visit (including baseline) and is the same at all non-missing visits, the language at the missing visit will be assumed to be unchanged.

	
Responder Status according to SGRQ Total Score	

• A participant will be considered a responder according to SGRQ total score if their SGRQ total score has decreased at least 4 units from the baseline SGRQ total score.

• A participant will be considered a non-responder if their SGRQ total score has decreased by less than 4 units, has not changed, or has increased compared to baseline.

• Missing data will be handled as detailed in Section 10.7.2.

	
Asthma Quality of Life Questionnaire (AQLQ)	
General	

• Details for how to score the AQLQ, including handling of missing data, are outlined in the AQLQ manual (June 2005).

• Changes from baseline in total score will be calculated for the converted scores.

• If the language of the AQLQ conducted at a post-treatment visit is different to the language used at Day 1 baseline, all AQLQ scores at that visit and all subsequent visits will be set to missing.

• If the language is missing at any visit (including baseline) and is the same at all non-missing visits, the language at the missing visit will be assumed to be unchanged.

	
Responder Status according to AQLQ Total Score	


• A participant will be considered a responder according to AQLQ total score if their AQLQ total score has increased at least 0.5 from the baseline AQLQ total score.

• A participant will be considered a non-responder if their AQLQ total score has increased by less than 0.5 units, has not changed, or has decreased compared to baseline.

• Missing data will be handled as detailed in Section 10.7.2.

	

Calculation of Daily eDiary Endpoints	
General	

• Efficacy endpoints based on diary assessments include E-RS total score, home trough FEV1 (L), PM FEV1, AM and PM PEF (L/min), and daily rescue medication use.

• The detailed derivations for diary data are provide in Section 5.2.2 for baseline value and Section 5.3.2 for post-baseline values.

• For AM and PM endpoints, if more than one assessment is available on the same calendar day, all assessments will be used in the calculation of the average for a given period.

	
Daily rescue medication use (puffs/day)	

• For a given day, the number of puffs will be the sum of the evening number of puffs (measures rescue medication use during the day) and following morning's number of puffs (measures rescue medication use during the previous night).

• If a participant only has one of these assessments then the number of puffs will be set to missing.

• If a participant has two morning assessments but no evening assessment or two evening assessments but no morning assessment then the daily rescue medication is the sum of the assessments

• If a participant has both an evening and a morning assessment and > 1 assessment at either of those timepoint, use the maximum value reported for the timepoint (i.e. number of puffs=max(morning) + max(evening))

	
Evaluating Respiratory Symptoms (E-RS)	


• The E-RS scoring instructions can be found in Appendix B of the User Manual [E-RS (Evaluating Respiratory Symptoms (E-RSTM) in COPD (E-RSTM: COPD) User Manual, Version 5.0. March 2016]

• Changes from baseline in total score will be calculated.

• If the language of the E-RS conducted post-randomization is different to the language used during the baseline period, all E-RS scores post-randomization will be set to missing.

• If the language is missing at any timepoint (including baseline period) and is the same at all non-missing timepoints, the language at the missing timepoint will be assumed to be unchanged.

	

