### **7.3.4. Strategy for Intercurrent (Post-Randomization) Events**

A “treatment policy” strategy will be used to handle all intercurrent events, including treatment discontinuation, use of rescue medication and temporary treatment switches.

Participants who discontinue treatment prematurely are encouraged to return for all clinic visits as planned. Data collected post treatment discontinuation will be included in all analyses, as well as data collected after rescue medication or treatment switches.

This analysis corresponds to the “de facto” analysis.

For responder analyses, a composite strategy will be used to handle the intercurrent event of premature withdrawal from study. The endpoint analyzed will therefore essentially be the percent of participants who do not prematurely discontinue from the study and meet the responder threshold. This is the equivalent to handling participants with missing data as non-responders (see Section 10.7.2).

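### One questionnaire in another language discards later SGRQ, AQLQ or ACQ scores that are back in the baseline language, and a Week 24 score lost this way counts as non-response

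*SAP*

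**What the plan says.** Section 10.6.3 gives each questionnaire its own language rule.

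- **SGRQ:** if the language differs from Day 1, "all SGRQ scores at that visit and all subsequent visits will be set to missing".
- **AQLQ:** the same, "all AQLQ scores at that visit and all subsequent visits will be set to missing".
- **ACQ, Visits 1 and 2 in the same language, a later visit different:** "all ACQ scores at the post-randomization visit and all subsequent visits will be set to missing".
- **ACQ, Visit 2 different from both Visit 1 and the later visits:** "all ACQ scores for all visits will be set to missing".
- **E-RS, post-randomization language different from the baseline period:** "all E-RS scores post-randomization will be set to missing".

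The responder definitions for SGRQ, AQLQ and ACQ-5 send missing data to Section 10.7.2, which says: "Participants with missing data at the analysis timepoint, regardless of treatment status, will be considered as a non-responder". The same section treats a missing baseline differently: "Participants with a missing baseline will have responder status as missing".

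Section 7.3.4 gives the rationale for the responder analyses: "a composite strategy will be used to handle the intercurrent event of premature withdrawal from study". It then describes this as equivalent to treating missing data as non-response and refers to Section 10.7.2.

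**The concern.** A language mismatch is a reason to distrust the form on which it occurred. It is not a reason to distrust a later form completed in the same language as baseline, and the SAP gives no other reason for dropping one. The rule nevertheless carries the deletion forward to the end of the study.

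Two things follow for SGRQ, AQLQ and ACQ-5. The mean-change MMRM in Section 7.3.5.1 loses observations that are comparable with baseline. The responder analysis goes further: a participant who is still in the study, and whose same-language Week 24 score may show an improvement above the threshold, is recorded as a non-responder because of an administrative error weeks earlier. The composite strategy in Section 7.3.4 does not cover that case, since it concerns people who leave the study.

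At stake are some valid patient-reported data, a small downward pull on responder rates, and an estimand statement that does not describe the endpoint actually derived.

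**Working it through.** The SAP states no figure that bears on this point, so there is none to reproduce. The check traces the rules through the visit schedule and then sizes the effect.

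**Step 1. Schedule trace.** Section 7.3.5.1 puts SGRQ, AQLQ and ACQ-5 at baseline and Weeks 4, 12 and 24. Suppose exactly one post-baseline form on an instrument is in another language.

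| Mismatch only at | Visits voided now | Of these, in baseline language | Voided if only the mismatched form is dropped |
|---|---|---|---|
| Week 4 | 4, 12, 24 | 12, 24 | 4 |
| Week 12 | 12, 24 | 24 | 12 |
| Week 24 | 24 | none | 24 |

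In the first two rows a same-language Week 24 score is lost, and Section 10.7.2 makes the participant a Week 24 non-responder. In the third row the current rule and the narrower one agree.

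For SGRQ and AQLQ this takes the rule to cover all post-randomization visits. The text says post-treatment visit, a term that Section 10.4.1 uses for the phase after treatment stops. The ACQ and E-RS rules say post-randomization, which is probably what is meant throughout.

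**Step 2. Composite strategy against missing-data rule.** For a participant who withdraws before Week 24, Sections 7.3.4 and 10.7.2 agree: non-responder. For a participant still in the study whose Week 24 score is language-voided, skipped or unscorable, the withdrawal composite in Section 7.3.4 does not apply, but Section 10.7.2 still gives non-response. The two are therefore not equivalent.

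**Step 3. E-RS.** Its rule also reaches back to post-randomization scores recorded before the change. Section 7.3.2 lists responder endpoints for SGRQ, AQLQ and ACQ-5 only, so the E-RS loss falls solely on the mean-change MMRM.

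**Step 4. Size per participant.** Section 5.4 gives the randomized counts: 174 + 69 + 21 + 114 + 58 = 436. With 1:1:1 allocation, 436 / 3 = 145.3 per arm. One forced non-response lowers an arm's responder rate by at most 1 / 145.3 = 0.69 percentage points. That maximum applies only if the participant would otherwise have responded.

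**Step 5. Illustration of the treatment comparison.** The SAP gives neither the share m of participants whose Week 24 score is voided only by an earlier mismatch, nor expected responder rates. Assume true rates of 60% (active) and 50% (placebo), so the odds ratio is (0.6/0.4)/(0.5/0.5) = 1.50, and let m run from 1% to 10%. Observed rate = true rate × (1 − m).

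| m | Participants per arm (145.3 × m) | Both arms affected: difference, points | Both arms affected: odds ratio | Active arm only: difference, points |
|---|---|---|---|---|
| 1% | 1.5 | 9.9 | 1.493 | 9.4 |
| 2% | 2.9 | 9.8 | 1.485 | 8.8 |
| 5% | 7.3 | 9.5 | 1.465 | 7.0 |
| 10% | 14.5 | 9.0 | 1.435 | 4.0 |

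For m = 5% in both arms: 0.60 × 0.95 = 0.570, 0.50 × 0.95 = 0.475, difference 9.5 points, odds ratio (0.570/0.430)/(0.475/0.525) = 1.465. The true difference is 10 points throughout.

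**The case against.** The strongest reply is that counting missing data as non-response is deliberate. Section 7.3.4 names the rule and points to Section 10.7.2, which lists missing data at the timepoint and withdrawal as separate cases and assigns non-response to both. Section 7.3.5.1 reports how many non-responders are due to missing data, and the same instruments are also analysed as continuous change, where a missing score is not a failure. This stands. Treating all missing scores in participants still in the study as missing at random would be a different design choice with its own assumptions, not a correction. It does not answer the narrower point that the language rule creates missingness where a usable score exists, and it leaves the sentence in Section 7.3.4 inaccurate.

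It is also fair to say that harm is not shown. Nothing says how often languages change, and a double-blind trial gives no evident reason for the frequency to differ by arm, so the last column of the illustration is a bound, not an expectation.

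Several stronger readings are tempting and are not supported:

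- A reader might infer that any language error makes a participant a non-responder. This cannot happen on E-RS, which has no responder endpoint. On ACQ, if Visit 2 is the odd one out, baseline is voided too and responder status is missing.
- A reader might infer that one wrong form wipes out every questionnaire. Each rule acts within its own instrument.
- A reader might infer that one stray diary entry deletes all 168 E-RS evenings. The rule compares the post-randomization language with the baseline-period language and does not say that a single entry triggers it. Nothing in the SAP describes switching from day to day on the device.
- A reader might infer that wrong values enter the mean-change models. The MMRM loses observations and precision; no erroneous values are added.

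**Conclusion.** The point holds as a minor one. For SGRQ and AQLQ, and for ACQ when Visits 1 and 2 share a language, the text discards later scores that are comparable with baseline. A Week 24 score lost this way becomes a non-response that the stated composite rationale does not cover. For E-RS the rule is too broad, with consequences for the mean-change analysis only.

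The per-participant ceiling of about 0.7 points assumes equal thirds of the 436 randomized. The total effect cannot be sized from the document. Under the assumed 60% and 50% rates, even 5% affected in both arms moves the odds ratio only from 1.50 to 1.465. All affected endpoints are exploratory, and the primary and secondary FEV1 analyses are untouched.

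**What to change.** In Section 10.6.3, within each instrument, set to missing only the scores recorded in a language different from baseline (for E-RS, only those diary days) and keep every score in the baseline language. In the same edit, replace post-treatment with post-randomization in the SGRQ and AQLQ sentences if that is what is meant.

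In Section 7.3.4, drop the claim of equivalence. State that non-response is assigned both after study withdrawal and for any other missing score at the timepoint, as Section 10.7.2 already does. Whether that second part should remain is a design choice and need not change.

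The cost is a few lines of SAP wording and a form-by-form language check in the derivation. With the Section 10.7.2 rule left as it is, responder denominators stay as planned.
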